5.0 ELIGIBILITY CRITERIA

5.1 Inclusion Criteria

- 5.1.1 Patients with histologically proven diagnosis of adenocarcinoma of the prostate stage N1, N2, N3, M1a, M1b, M1c with \leq 5 metastatic lesions. If the diagnosis of metastasis in the lymph node is based solely on imaging CT scan or MRI, the longitudinal diameter of the lymph node has to be \geq 2.0 cm. If the lymph node is positive on PET or Prostascint scan, the longitudinal diameter of the lymph node on CT scan or MRI has to be \geq 1.5 cm.
- 5.1.2 Patients who have measurable disease must have had X-rays, scans or physical examination used for tumor measurement completed within 28 days prior to registration. Patients must have non-measurable disease assessed within 42 days prior to registration.
- 5.1.3 Patients must have had documented PSA level of > 2 prior to onset of androgen deprivation.
- 5.1.4 Patients might have received up to 36 weeks of adjuvant androgen deprivation therapy and up to 36 weeks of androgen deprivation therapy for metastatic disease prior to enrollment to this study. Patients may be on androgen deprivation for metastatic disease at the time of enrollment to the protocol. Adjuvant therapy must have been completed at least 2 years before

androgen deprivation for metastatic disease and patients must remain hormone sensitive.

- 5.1.5 Prior radiation therapy for metastatic disease is not allowed.
- 5.1.6 Prior chemotherapy for metastatic disease is not allowed. Prior neoadjuvant and adjuvant chemotherapy is allowed. Patients must have recovered from all acute side-effects related to previous systemic therapy.
- 5.1.7 Patients are allowed to receive one prior systemic non-chemotherapeutic treatment (i.e. immunotherapy, receptor tyrosine kinase inhibitor, antiangiogenic agent, differentiating agent) for recurrent or metastatic disease. Patients must have recovered from all acute side-effects related to previous systemic therapy.
- 5.1.8 Use of bisphosphonates is allowed at the discretion of treating physician
- 5.1.9 Patients must be at least 18 years of age.
- 5.1.10 Patient must be capable of understanding the nature of the trial and must give written informed consent.
- 5.1.11 Patients must have a WHO Performance status of 0, 1, or 2.
- 5.2 Exclusion Criteria
 - 5.2.1 Patients with unstable or severe intercurrent medical conditions or active, uncontrolled infection.
 - 5.2.2 Patients with history of orchiectomy.

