 - 5.2.3 Patients undergoing therapy with other investigational agents. Patients must have recovered from all acute effects of previously administered investigational agents and sufficient time must have elapsed since last administration to ensure the drug interactions not occur during this study.
 - 5.2.4 Patients with a history of brain metastases or who currently have treated or untreated brain metastases.
 - 5.2.5 Patients who have demonstrated refractoriness to hormone therapy with LHRH agonist. Refractoriness is defined as occurrence of one of the following while on therapy with LHRH agonist: Increase in PSA by 25% over baseline (to at least > 2 ng/ml) on two consecutive PSA measurements, 20% increase in the sum of longest diameters of target measurable lesions over smallest sum observed (over baseline if no decrease during therapy) using the same techniques as baseline, clear worsening of any non-measurable disease, reappearance of any lesion that had disappeared, appearance of any new lesion.

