6.0 TREATMENT PLAN

Treatment will be given according to the Schema described in section 6.1. A treatment may be stopped for up to 4 weeks to allow for recovery from toxicities. Patients unable to safely resume treatment at that point will be taken off study. 12 weeks constitutes one cycle of hormone therapy.

6.1 Treatment schedule:

- 6.1.1 Patients will begin radiation therapy only after they have demonstrated evidence of PSA normalization after initiation of androgen deprivation therapy (stable or declining PSA level of \leq 4 (or stable or declining PSA \leq pre-treatment level whichever is smaller) on two consecutive measurements. Patients who do not meet these criteria will be taken off protocol.
- 6.1.2 Patients will be divided into two strata:

Stratum 1:

a) Patients who are not on androgen deprivation therapy at the time of enrollment to the protocol will begin androgen deprivation and start radiation therapy after PSA normalization (see section 6.1.1)

b) Patients who are already treated with androgen deprivation therapy at the time of enrollment to the protocol (see 5.1.4) will continue androgen deprivation therapy and begin radiation after meeting criteria for PSA normalization (see section 6.1.1). Radiation therapy will be finished before 36 weeks (± 2 weeks) of hormone therapy is completed.

Stratum 2:

Patients who are enrolled on the protocol towards the end (or after completion) of 36 weeks (\pm 2 weeks) of androgen deprivation so radiation treatment cannot be finished before the completion of 36 weeks of androgen deprivation therapy can still initiate and/or complete radiation therapy as long as their serum testosterone level remains at the castrated levels (<50 ng/dL) and they meet the criteria for PSA normalization (section 6.1.1). Patients will not receive more than 36 weeks of androgen deprivation therapy.

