- 9.2.3 Complete response (CR): Complete disappearance of all measurable and non-measurable disease. No new lesions. No disease-related symptoms. For patients status post previous prostatectomy PSA level <0.2. For patients with remaining prostate declining or stable PSA level <1. All measurable, and non-measurable lesions and sites must be assessed using the same technique as baseline.

- 9.2.4 Stable/No response: Does not qualify for CR, PR, or progression. All measurable and non-measurable sites must be assessed using the same techniques as baseline.
- 9.2.5 Progression: One or more of the following must occur **at the time of androgen deprivation therapy:** Increase in PSA by 25% over baseline (to at least > 2 ng/ml), 20% increase in the sum of longest diameters of target measurable lesions over smallest sum observed (over baseline if no decrease during therapy) using the same techniques as baseline, clear worsening of any non-measurable disease, reappearance of any lesion that had disappeared, appearance of any new lesion/site, failure to return for evaluation due to death, deteriorating condition (unless clearly unrelated to this cancer).
- 9.2.6 a) Non-measurable disease does not affect objective status except in determination of CR (must be absent a patient who otherwise has CR, but who has non-measurable disease present or not assessed, will be classified as having a PR), and in determination of progression (if new sites of disease develop or if unequivocal progression occurs in the opinion of the treating physician).

b) Appearance or worsening of pleural effusions do not constitute unequivocal progression unless cytologically proven of neoplastic origin.

c) For "scan-only" bone disease, increased uptake in previously seen lesions does not constitute clear worsening.

d) In cases for which initial tumor flare reaction is possible (hypercalcemia, increased bone pain, erythema of skin lesions), either symptoms must persist beyond 4 weeks or there must be additional evidence of progression.

e) Lesions that appear to increase in size due to presence of necrotic tissue will not be considered to have progressed.

9.2.7 Unknown: Progression has not been documented and one or more measurable or non-measurable sites have not been assessed.

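### PSA progression on androgen deprivation is measured from an undefined baseline, not the lowest PSA, so PFS and time to treatment failure can miss an escape already above the relapse level

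*Combined protocol and SAP*

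**What the plan says.** All references are to the combined protocol and SAP.

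- **9.2.5 (progression on ADT).** The PSA limb reads "Increase in PSA by 25% over baseline (to at least > 2 ng/ml"). The tumor-size limb of the same sentence takes a 20% increase "over smallest sum observed (over baseline if no decrease during therapy"). No confirming PSA is required, and the events must occur during ADT.
- **5.2.5 (refractoriness exclusion).** It uses the same reference with a confirmation: "Increase in PSA by 25% over baseline (to at least > 2 ng/ml) on two consecutive PSA measurements".
- **Meaning of baseline.** Neither section defines it. The response rule in 9.2.1 equates baseline with the pre-treatment PSA. The calendar in section 8.0 takes a PSA within 14 days of day 1 of cycle 1, which may already be suppressed in a patient who joins on ADT.
- **Eligibility.** 5.1.3: "Patients must have had documented PSA level of > 2 prior to onset of androgen deprivation". 5.1.4 adds that patients must still be hormone sensitive, without a PSA rule.
- **6.1.1 (before radiation).** Patients must have "demonstrated evidence of PSA normalization after initiation of androgen deprivation therapy (stable or declining PSA level of" 4 or less (or the pre-treatment value or less, whichever is smaller) "on two consecutive measurements. Patients who do not meet these criteria will be taken off protocol".
- **Use of the progression rule.** PFS (9.4.2) cites 9.2.5. Time to treatment failure (9.4.3) and removal from treatment (6.3.1) both rest on disease progression.
- **Primary endpoint.** It uses 9.2.8 instead: PSA above the smaller of the pre-therapy value and 10. Under 9.4.4 its clock starts at the last bicalutamide dose or last radiation day, whichever is later.

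**The concern.** The protocol's background expects most patients to respond to ADT at first. A later loss of response would then show as a PSA rise from a low nadir. A rule tied to the pre-ADT level sees nothing until the PSA has climbed past where it began. The size limb avoids this by using the smallest sum; the PSA limb does not, although PSA is the marker on which the trial is built.

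Two things are at stake. PFS and time to treatment failure could run on through a PSA failure under castration. The same failure could then be recorded as a very early relapse after ADT, so the two sets of endpoints would describe one course in conflicting ways. If baseline instead means the enrollment value, patients in different strata are held to different standards.

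**Working it through.** **1. The plan's own figure.** Section 10.0 gives 83% power for 28 patients, medians of 9 versus 16 months, one-sided 0.05, accrual A = 24 and follow-up F = 12 months. With exponential hazard λ and uniform accrual, P(event) = 1 − [exp(−λF) − exp(−λ(A+F))]/(λA). Expected events are 22.9 under the null and 17.6 under the alternative. Power = Φ((ln(16/9) − 1.645/√22.9) × √17.6) = 0.835. The critical median is 9 × exp(1.645/√22.9) = 12.7 months, against the stated 13. The figure reproduces, and none of its inputs involves 9.2.5.

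**2. Baseline read as pre-ADT PSA (B).** The 9.2.5 trigger is 1.25B; the 9.2.8 relapse level is min(B, 10). Since 1.25B > B ≥ min(B, 10) for any positive B, the on-ADT trigger is above the relapse level for every eligible patient. Because B > 2, 1.25B > 2.5, so the 2 ng/ml floor never binds.

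The nadirs below are illustrative. The last column applies the same 25% and 2 ng/ml limits to the nadir.

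| Pre-ADT PSA | Nadir | 9.2.5 trigger | Multiple of nadir | 9.2.8 level | Nadir-based trigger |
|---|---|---|---|---|---|
| 3 | 0.1 | 3.75 | 37.5 | 3 | >2 |
| 10 | 0.5 | 12.5 | 25 | 10 | >2 |
| 20 | 0.5 | 25 | 50 | 10 | >2 |
| 40 | 0.5 | 50 | 100 | 10 | >2 |
| 40 | 4 | 50 | 12.5 | 10 | 5 |
| 100 | 0.5 | 125 | 250 | 10 | >2 |

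A patient with pre-ADT PSA 40 who reaches 15 on ADT has not progressed by PSA (15 < 50), yet is above the relapse level (15 > 10) when ADT ends. His time to PSA relapse is then close to zero. 9.2.5 is confined to the ADT period, so it does not pick him up later.

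**3. Baseline read as enrollment PSA.** A patient with pre-ADT PSA 40 who joins on ADT at 1.0 has 1.25 × 1.0 = 1.25, so the floor governs and he progresses at >2. The same course in Stratum 1a, enrolled at 40, needs 50. The floor binds only when baseline is below 2/1.25 = 1.6, so it has work to do only on this reading. The text does not settle which reading is meant.

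**4. What else could catch the escape.**
- 6.1.1 acts before radiation. Nothing in it applies once radiation has begun.
- If a Stratum 1a patient passes it at week 12 (an assumed time), 36 − 12 = 24 weeks of ADT remain.
- After enrollment, the calendar schedules tumor assessment only at the end of ADT or radiation, whichever is later, and at PSA relapse. PSA every 4 weeks is the only routinely scheduled disease measure in between.
- 9.2.6(c) does not count increased uptake in known scan-only bone lesions.

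**5. Direction of any effect on the primary test.** The documents give no escape rate, so this is illustration only. Assume that 5%, 10% or 20% of the analysed patients escape and relapse with a median of 1 to 3 months after the clock starts (40,000 simulations each). Power at a 16-month median in the rest is 74–76%, 62–67% or 38–45%. Type I error falls to about 0.03, 0.02 or below 0.01. The push is toward finding no effect.

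**The case against.** **Other screens exist.** A reader might infer that 5.2.5 alone guards against lost hormone sensitivity, so refractory patients pass freely into the trial. The documents do not support that. 5.1.4 requires that "androgen deprivation for metastatic disease and patients must remain hormone sensitive"; 6.1.1 stops radiation unless the PSA is low and not rising on two measurements; 6.3.2 removes patients who never normalize; and 5.2.5 and 9.2.5 have non-PSA limbs. A clearly rising PSA before radiation should be stopped. One might construct a patient at 0.5, then 3.0 and 3.0, who passes 6.1.1. That is doubtful, since the first 3.0 is neither stable nor a decline. What stands is that stable is undefined, the two values are not tied to the start of radiation, and an escape beginning after the check is untouched.

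**Escaping patients may not be analysed.** Section 9.0 limits the response and relapse analyses to patients who complete radiation and 12 weeks of ADT on protocol. One registered at week 28 has at most 36 + 2 − 28 = 10 weeks left. Section 10.0 says the initial analysis includes all patients, so their inclusion is unresolved. The near-zero relapse time applies only to a patient who is analysed.

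**Limited weight.** Section 10.0 does not list PFS or time to treatment failure as secondary endpoints; PFS is in the long-term follow-up objective. That stands and lowers the stakes. Section 10.1 does, however, plan to report progression status and a Kaplan-Meier estimate of time to progression.

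**A design choice.** Nothing requires the PSA and size limbs to share a reference. True, but an undefined baseline and an on-ADT trigger above the off-ADT relapse level go beyond preference.

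**Conclusion.** The concern holds for the endpoint definitions. On the pre-ADT reading, the PSA trigger exceeds the relapse level in every eligible patient. A comparison with a fixed 10 might suggest that this happens only above a PSA of 8 (1.25 × 8 = 10), but the relapse level is the smaller of the two values, so there is no such cut-off. On the enrollment reading, the trigger depends on when the patient joined.

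On the pre-ADT reading, and for Stratum 1a on either, PFS and time to treatment failure therefore miss a PSA escape from a low nadir unless another limb fires or, for time to treatment failure, treatment stops early. The main exposure is escape that begins after the 6.1.1 check has been passed.

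A reader might also infer that the 83% power is wrong or that the trial is biased toward claiming activity. Neither follows: the power reproduces from its own inputs, and undetected escape would pull the primary test toward no effect. How often escape occurs cannot be judged from the documents, and the illustrative losses of power rest wholly on assumed shares and medians.

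**What to change.** For PFS and time to treatment failure only, write the PSA limb into 9.4.2 and 9.4.3: a 25% rise, to above 2 ng/ml, over the lowest value observed on ADT (over baseline if there was no decrease), on two consecutive measurements as 5.2.5 already requires. State whether the event is dated at the first or the confirming value, and whether on-ADT values before registration count toward the lowest value. Define baseline for Strata 1a, 1b and 2.

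The cost is wording. PSA is already drawn every 4 weeks, so no visits or samples are added. PFS becomes slightly less favourable. The primary endpoint and sample size do not change: an analysed patient who escapes on ADT will still show an early relapse, but PFS will now also record the failure.

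Sections 5.2.5 (eligibility), 6.1.1 (start of radiation) and 6.3.1 (removal from treatment) use related PSA rules that agree neither with each other nor with 9.2.8. The sponsor should reconcile them. No clinical rule is proposed here for any of them, and placing the endpoint wording in 9.4 keeps it separate from removal from treatment.

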8.0 STUDY PARAMETERS AND CALENDAR

Assessment	Prior to Enrollment	Day 1 of each cycle [*]	Every 4 weeks until PSA relapse	At the time of PSA relapse
History and Physical Exam	X ¹	X ²		
Weight and WHO PS	X ¹	X ²		
Toxicity using CTC v3.0		X ²		
CBC, Diff, Plts, Na, K, Cl, CO ₂ , Creatinine, BUN, glucose, Calcium, phosphorus, albumin, LDH, SGPT (ALT), SGOT (AST), Alkaline Phos, Total Bilirubin	X ¹ X ¹	X ²		
EKG	X ³			
Chest X-Ray	X ³			
PSA	X ³		X^7	
Serum testosterone	X ³		X ⁸	
Tumor Measurements (measurable disease)	X ⁴	X^6		Х
Tumor Evaluation (evaluable disease)	X ⁵	X ⁶		Х
Treatment: LHRH agonist (goserelin or leuprolide)		q 4 weeks x 9 doses or q 12 weeks x 3 doses (total duration of androgen deprivation- see section 6.1) ⁹		
Treatment: bicalutamide		daily x 36 wee androgen depri	ks (total dur vation- see	ation of section 6.1) ⁹

Assessment	Prior to Enrollment	Day 1 of each cycle [*]	Every 4 weeks until PSA relapse	At the time of PSA relapse
Treatment: Radiation		daily x 2-7 weeks during or after completion of androgen deprivation therapy (see section 6.1)		

*Each cycle = 12 weeks

¹Within 7 days of d1 of cycle #1 (can be done on d#1 cycle #1)

²Except cycle 1 if done within 7 days of d1 of cycle #1

³Within 14 days of d1 of cycle #1

⁴Within 28 days of d1 of cycle #1

⁵Within 42 days of d1 of cycle #1

⁶At the time of completion of 36 weeks of androgen deprivation therapy or radiation therapy (whichever comes later) ⁷ Can be done on the day of clinic visit or up to 14 days before or after.

7 PSA; every 4 weeks for 2 years, and every 3mos after year 2, every 6 mos. thereafter or until relapse which ever occurs first.

⁸ Four weeks after the first LHRH injection, afterwards no repeat measurements will be done until the day of the last LHRH injection, and then monthly until the normalization of testosterone levels or resumption of androgen deprivation therapy (whichever comes first). Testosterone level will also be drawn to confirm castrated levels in patients who completed 36 weeks of androgen ablation and are considered for radiation therapy (see section 6.1.2.) To simplify schedule, testosterone level can be drawn on the same day that PSA test

 9 ± 2 weeks

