- 9.2.8 PSA relapse after completion of initial 36 weeks of androgen deprivation therapy is defined as an increase in PSA value to above pre-therapy level or > 10 (whichever is smaller). For example patient with pre-treatment PSA level of 40 will resume androgen deprivation therapy when PSA level is > 10, patient with pre-treatment PSA level of 3 will resume androgen deprivation therapy when PSA level is > 3.
- 9.3 Best Response: This is calculated from the sequence of objective statuses
 - a) CR: Two or more objective statuses of CR a minimum of four weeks apart documented before progression or symptomatic deterioration.
 - b) PR: Two or more objective statuses of PR or better a minimum of four weeks apart documented before progression or symptomatic deterioration, but not qualifying as CR.
 - c) Unconfirmed CR: One objective status of CR documented before progression or symptomatic deterioration but not qualifying as CR or PR.
 - d) Unconfirmed PR: One objective status of PR documented before progression or symptomatic deterioration but not qualifying as CR, PR or unconfirmed CR.
 - e) Stable/no response: At least one objective status of stable/no response documented at least six weeks after registration and before progression or symptomatic deterioration, but not qualifying as anything else above.
 - f) Increasing disease: Objective status of progression or symptomatic deterioration within twelve weeks of registration, not qualifying as anything else above.
 - g) Inadequate assessment, response unknown: Progression or symptomatic deterioration greater than twelve weeks after registration and no other response category applies.
- 9.4 Time-Related Endpoint Definitions
 - 9.4.1 Survival: Defined as the time from registration to time of death due to any cause. If a patient is not known to have died, survival time is censored at the time of last follow-up.
 - 9.4.2 Progression-free survival: Defined as the time from registration to the first observation of disease progression (as defined in 9.2.5) or death due to any cause. If a patient has not progressed or died, progression-free survival is censored at the time of last follow-up.
 - 9.4.3 Time to treatment failure: Defined as the time from registration to the first observation of disease progression, death due to any cause, or early discontinuation of treatment. If failure has not occurred, failure time is censored at the time of last follow-up.

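### On the calendar's scan schedule CR cannot be confirmed and PR is confirmable only through PSA relapse; the plan does not say which best-response rows form the objective response rate, and PRNM has no row

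*Combined protocol and SAP*

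**What the plan says.** **Schedule.** In section 8.0 both tumor rows are marked at baseline, under the column "Day 1 of each cycle" and at PSA relapse. Footnote 6 ties the middle mark to one time: completion of 36 weeks of ADT or of radiation, whichever is later. At relapse the patient leaves the protocol, and only chart review follows (6.1.3).

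**Best response (9.3).** Two categories need a repeat: "CR: Two or more objective statuses of CR a minimum of four weeks apart documented before progression or symptomatic deterioration" and "PR: Two or more objective statuses of PR or better a minimum of four weeks apart documented before progression or symptomatic deterioration". A single finding goes to a lower row, for example "Unconfirmed CR: One objective status of CR documented before progression or symptomatic deterioration but not qualifying as CR or PR", and there is a matching Unconfirmed PR row.

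**PSA limits.** CR requires PSA below 0.2 after prostatectomy; otherwise, "For patients with remaining prostate declining or stable PSA level <1" (9.2.3). PSA relapse "is defined as an increase in PSA value to above pre-therapy level or > 10 (whichever is smaller") (9.2.8). For entry, "Patients must have had documented PSA level of > 2 prior to onset of androgen deprivation" (5.1.3).

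**Other statuses.** Progression counts only during ADT (9.2.5). PRNM is defined in 9.2.1 by a PSA fall of more than 50% without progression of non-measurable disease or new lesions. PR is restricted to patients with a measurable lesion (9.2.2). Stable/No response is the remainder: "Does not qualify for CR, PR, or progression" (9.2.4). Section 9.2.6a assigns PR to a patient who would be CR but for non-measurable disease that is present or unassessed.

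**Reporting.** Section 10.1 reports response for all eligible registered patients. Section 9.0 limits the response analysis to those who complete radiation and 12 weeks of ADT on protocol. Neither section says which 9.3 rows make up the rate in Objective 2.

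**The concern.** The confirmation rule and the scan calendar do not fit each other. A patient who responds and never relapses has one post-baseline tumor assessment and cannot be confirmed. The second assessment is triggered by relapse, when PSA is too high for CR. The ranking is then perverse: a complete responder who relapses with lesions still absent can become a confirmed PR, while the same patient without relapse stays in the Unconfirmed CR row.

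The plan also leaves open whether unconfirmed rows count as responses. If only confirmed rows count, CR is zero on scheduled scans and non-relapsing responders drop out. If unconfirmed rows count, the rate is a different quantity. That choice would be made after the data are seen.

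PRNM adds a second gap. Section 6.1.2 expects most sites to be bone or lymph node, and 9.1.2 classes bone disease as non-measurable, so the category without a row may not be rare.

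**Working it through.** **1. Can the relapse scan be CR?** The relapse threshold is min(pre-ADT PSA, 10), and pre-ADT PSA is above 2. For pre-ADT values of 2.01, 3, 5, 10 and 40 the thresholds are 2.01, 3, 5, 10 and 10. All exceed the CR limits of 0.2 and 1. Section 6.1.3 speaks of reaching the level and 9.2.8 of exceeding it; either way PSA is above 2. Two CR statuses on scheduled scans are impossible.

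**2. All status sequences.** Visit A is the end of ADT or radiation. Visit B is PSA relapse, at least four weeks later.

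| A | B | Best response under 9.3 |
|---|---|---|
| CR | none | Unconfirmed CR |
| PR | none | Unconfirmed PR |
| Stable | none | Stable/no response |
| CR | PR | PR |
| CR | Stable | Unconfirmed CR |
| PR | PR | PR |
| PR | Stable | Unconfirmed PR |
| Stable | PR | Unconfirmed PR |
| Stable | Stable | Stable/no response |

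Confirmed PR always needs visit B. It is available there because 9.2.2 sets no PSA limit for PR and 9.2.5 confines progression to ADT. If PSA relapse were treated as progression, PR could not be confirmed on scheduled scans at all; the table takes the more lenient reading.

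**3. Patients with only non-measurable disease and a PSA fall above 50%, no progression and no new lesions.**
- PSA above the CR ceiling: not CR; not PR by 9.2.2; not progression. Section 9.2.4 read literally gives Stable/No response.
- PSA below the ceiling, no symptoms, lesion persisting: 9.2.6a points to PR, but 9.2.2 does not allow it.

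**4. Scale.** The inputs are from section 10: exponential relapse time, medians of 9 and 16 months, 28 patients, 24 months of accrual and 12 months of follow-up. With λ = ln 2/median and relapse follow-up uniform from F to F + 24 months,

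share not relapsed = [exp(−Fλ) − exp(−(F + 24)λ)] / (24λ).

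*Check against the plan's power, F = 12.* Shares relapsed are 0.819 and 0.630, so expected events are 28 × 0.819 = 22.9 and 28 × 0.630 = 17.6. Power = Φ[(ln(16/9) − 1.645/√22.9) × √17.6] = 0.835, against the stated 83%. The model is reproduced.

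*Follow-up from end of therapy, F = 12.*
- Median 9: λ = 0.0770; (0.397 − 0.0625)/1.848 = 0.181.
- Median 16: λ = 0.0433; (0.595 − 0.210)/1.040 = 0.370.

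*Follow-up from registration, all 36 weeks (8.28 months) of ADT on study, F = 12 − 8.28 = 3.72.*
- Median 9: (0.751 − 0.118)/1.848 = 0.342.
- Median 16: (0.851 − 0.301)/1.040 = 0.529.

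*Four-week gap (0.92 months).* The ceiling on confirmation is exp(−0.92λ) minus the share not relapsed:
- from end of therapy: 0.932 − 0.181 = 0.751 and 0.961 − 0.370 = 0.591;
- from registration: 0.932 − 0.342 = 0.590 and 0.961 − 0.529 = 0.432.

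These ceilings take the first scan as the start of the relapse clock and assume relapse time is independent of response.

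**The case against.** The strongest reply is that little is lost. Section 9.3 already has rows for single-assessment responses, and 10.1 makes them visible, so a reader could compute the measurable-disease rate either way. The rate is not among the secondary endpoints listed in section 10, and no test, decision rule or sample size uses it. Counting confirmed or unconfirmed responses is a convention. All of that is correct and limits the weight of the point. It does not say which rows form the rate, and it does not give PRNM a row.

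The calendar heading could also mean scans at every cycle, in which case confirmation during ADT might be possible. Footnote 6 is specific to these marks and is the natural reading, but the two need reconciling. Unscheduled scans are not forbidden and could add confirmations, so the impossibility holds for scheduled scans only.

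A reader might infer that every bone-only PSA responder is recorded as stable. The documents do not support that: 9.2.6a points some of them to PR, and the title of PRNM lets it be read as a kind of PR. What stands is an omission and a conflict with 9.2.2.

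A reader might also turn the shares into numbers of lost responders. The documents do not give the number of patients with measurable disease, so no such count is justified.

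**Conclusion.** The point holds for the objective response rate of Objective 2. On the footnote 6 schedule, confirmed CR cannot occur on scheduled scans, and PR is confirmable only through a relapse at least four weeks after the end-of-therapy scan. The share with no relapse scan is about 18% to 37% with follow-up from end of therapy and about 34% to 53% with follow-up from registration. Section 10 does not say when follow-up starts, so both ranges are shown. Within each, the share rises with the median, so confirmation becomes less available the better the treatment works. Longer follow-up would lower it.

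These figures limit confirmation; they are not response rates. It would be wrong to infer that no response can be confirmed, or that the trial's main conclusion is at risk: PR can be confirmed after relapse, and time to PSA relapse and PSA response do not depend on these rows. The plan should be corrected, but the fault does not threaten the primary analysis.

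**What to change.** 1. In 9.3, define the objective response rate as CR or PR at the scheduled end-of-ADT/radiation assessment. Label it as not confirmed by a second scan, and state that the confirmation rules in 9.3a and 9.3b do not apply to it.
2. Use as denominator all eligible registered patients with measurable disease, in line with 10.1, and count those removed early or not assessed as non-responders. If the 9.0 evaluable set is also reported, show it second. State that, read literally, it leaves out Stratum 2 patients without 12 weeks of ADT on protocol, as well as early failures, whose omission can inflate the rate.
3. Add PRNM as its own category in 9.2.4 and 9.3, reported separately from measurable-disease CR and PR. Reconcile 9.2.6a with 9.2.2 for patients with only non-measurable disease.
4. Reconcile the calendar column heading with footnote 6 for the two tumor rows.

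The cost is wording only, with no added scans or patients. The rate will be unconfirmed on imaging and may be slightly lower with the all-registered denominator.
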